### **8.4 Prior and Concomitant Medications**

Concomitant medications for this study are defined as any medication the patient is receiving at the time of enrollment, or any new medication received by the patient after the date of enrollment. Prior medications are medications with a stop date prior to date of study enrollment. Medications will be coded using the WHO Drug Dictionary. The versions used for the coding will be noted as a footnote in the tables and listings.

The number and percentage of patients who receive prior and concomitant medications will be summarized, separately, by the WHO Drug Dictionary Anatomical Therapeutic Chemical 4th level (ATC-4) and the preferred name. If the 4th level term is not available, the next available level (e.g., ATC-3) will be used.

ATC-4 and preferred name will be presented in descending frequency first and then alphabetically if there are ties. Each patient will contribute at most one count per summarization category. In other words, if a patient has more than one medication with same preferred name, the patient will be counted only once for that preferred name. Similarly, if a patient has more than one medication for an ATC-4 level, the patient will be counted only once in that ATC-4 level and preferred name.

Prior and concomitant medications will be presented by patient in a data listing. The listing will show the verbatim medication/therapy, the ATC-4 term, preferred name, indication, medication start date, medication end date (or ongoing), dose, dose unit, frequency, and route.

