### Imputation Criteria for Missing/Partial Dates

Variable	Missing Day	Missing Month or Day and Month	Missing Year, Month and Year, or Day and Year	Missing Day, Month, Year
----------	-------------	--------------------------------	---	--------------------------

AE/Medication Start Date	Assign to the first of the month (i.e. UNK-JAN-2019 becomes 01-JAN-2019)	Assign to the month of 'June' (i.e. 01-UNK-2019 becomes 01-JUN-2019), provided the imputed date is on or after the patient's baseline study treatment date; otherwise, the subsequent month after study treatment will be used.	Assign to year of study treatment will be used (i.e. 01-JAN-UNK becomes 01-JAN-2019), provided the imputed date is on or after the patient's study treatment date; otherwise, the subsequent year after treatment will be used.	Assign to baseline study treatment date
AE/Medication End Date	Assign the last day of the month (i.e. UNK-JAN-2019 becomes 31-JAN-2019).	Assign to the subsequent month after the start date.	Assign to the year of baseline study treatment (i.e. 01-JAN-UNK becomes 01-JAN-2019), provided the imputed date is after the start date; otherwise, the subsequent year after start date will be used.	Assumed medication is ongoing; no imputation

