## 12 Interim Analysis and Data Monitoring

An interim analysis is planned for 23 August 2023, the last day study day prior to the first scheduled Bridging Visit (see protocol for more information). The purpose of this analysis is to support a regulatory submission to the European Medicines Agency (EMA).

All efficacy analyses, demographics, medical history, concomitant procedures, prior medications, and concomitant medications will be created for this analysis but will only include patients that have completed or early discontinued from the study as of 23 August 2023. The results of this analysis will not be considered for the purposes of modifying the study.

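### SAP 11.2 applies AE-oriented date imputation to medications, so some medicines with partial stop dates will land in the wrong prior or concomitant table (minor)

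*SAP*

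**What the plan says.** The imputation table in SAP 11.2 has two rows, "AE/Medication Start Date" and "AE/Medication End Date", each serving both kinds of record.

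Start dates:
- Day missing: first of the recorded month.
- Month missing: June of the recorded year, "provided the imputed date is on or after the patient's baseline study treatment date; otherwise, the subsequent month after study treatment will be used".
- Year missing: the year of study treatment, "provided the imputed date is on or after the patient's study treatment date; otherwise, the subsequent year after treatment will be used".
- Wholly missing: "Assign to baseline study treatment date".

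Stop dates:
- Day missing: last day of the recorded month.
- Month missing: "Assign to the subsequent month after the start date".
- Year missing: the baseline treatment year if that falls after the start, otherwise the year after the start.
- Wholly missing: treated as ongoing, with no imputation.

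SAP 8.4 then sorts the records: "Prior medications are medications with a stop date prior to date of study enrollment". Concomitant medicines are those being taken at enrollment or newly received after it. The two groups are tabulated separately, and SAP 12 puts both tables in the interim package for the EMA submission ("prior medications, and concomitant medications will be created for this analysis"). SAP 11.2 also says that listings show dates as collected.

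**The concern.** Moving an AE with an uncertain onset to on or after first dose is cautious, because the event is then counted as treatment-emergent. Medicines differ: many began, and some ended, before the trial. For them the same rule can contradict a recorded year and can place the start after a recorded stop. An old medicine can then look newly started, which Protocol 7.4 discourages except to treat an AE.

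The stop-date cells matter more, because SAP 8.4 classifies by stop date. The missing-month cell does not mention the recorded stop year, and the missing-year cell supplies a year that the record does not support. In a single-arm trial with BMI endpoints, a reader will use the medication tables to see what else the children were taking. A table that disagrees with the listing behind it weakens that check.

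**Working it through.** **Inputs.** The rules are from SAP 11.2, the classification from SAP 8.4, and the planned 10-15 patients from SAP 3.4. First dose is assumed to be 10 March 2022; the Protocol synopsis estimates first enrollment in February 2022. Enrollment and first dose share a day, because the first dose is given at the enrollment visit (Protocol 5.1.3).

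**The plan's own examples.** Applied as written, the rules reproduce them: UNK-JAN-2019 becomes 01-JAN-2019 as a start and 31-JAN-2019 as a stop; 01-UNK-2019 becomes 01-JUN-2019; 01-JAN-UNK becomes 01-JAN-2019.

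**Two readings.** The missing-month stop rule can be read literally (the month after the start, whatever stop year was recorded) or as keeping the recorded stop year.

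| Case | Recorded start | Recorded stop | Literal reading | Year kept |
|---|---|---|---|---|
| 1 | 15 Jan 2020 | UNK-2022 | Feb 2020, prior | Feb 2022, prior |
| 2 | 10 May 2021 | 20-JAN-UNK | 20 Jan 2022, prior | same |
| 3 | 10 May 2019 | 01-OCT-UNK | 1 Oct 2022, concomitant | same |
| 4 | UNK-2019 | UNK-2020 | start Apr 2022, stop May 2022, concomitant | start Apr 2022, stop May 2020, prior |
| 5 | 15 Jan 2021 | UNK-2023 | Feb 2021, prior | Feb 2023, concomitant |
| 6 | UNK-2018 | 1 Sep 2019 | start Apr 2022, prior | same |

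- **Case 1** is called prior on both readings. From 10 March to 31 December 2022 there are 22+30+31+30+31+31+30+31+30+31 = 297 days, so 297/365 = 81% of the possible stop dates are not before enrollment.
- **Case 2** is called prior on both readings. If the true stop was 20 January 2023, the medicine was taken for 297+19 = 316 days after first dose.
- **Case 3** errs the other way if the true stop was 1 October 2019.
- **Case 4** is wrong only on the literal reading. The stop was no later than 31 December 2020, which is 365+31+28+10 = 434 days before first dose. With the year kept the class is right, but the start follows the stop.
- **Case 5** is wrong only on the literal reading.
- **Case 6** keeps the right class by its stop date, but the imputed start falls after the recorded stop.

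**Illustrative simulation.** 100,000 records were drawn per pattern. Every range is an assumption: enrollment spread over 240 days from 1 February 2022, starts up to three years before first dose, courses up to three years, and stops beyond Week 52 redrawn within the trial year. The replacement rule takes the latest stop consistent with the recorded parts, or ongoing if the year is unknown. Each cell gives two shares: truly prior medicines tabulated as concomitant / truly concomitant medicines tabulated as prior.

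| Missing part | Current rule | Replacement |
|---|---|---|
| None (complete stop) | 0% / 0% | 0% / 0% |
| Stop day | 3% / 0% | 3% / 0% |
| Stop month and day, literal | 0% / 92% | 25% / 0% |
| Stop month and day, year kept | 14% / 22% | 25% / 0% |
| Stop year | 52% / 33% | 100% / 0% |
| Whole stop date | 100% / 0% | 100% / 0% |

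These are error rates given that a date is partial. The documents do not say how often that happens, so no overall rate can be computed.

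**Weight of one error.** One child moves a table row by 1/15 = 6.7 to 1/10 = 10 percentage points.

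**The case against.** The other side has four good arguments.

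1. The most striking errors (Cases 4 and 5) need the literal reading. The start-date example in the same column keeps the recorded year, so the kinder reading is plausible, and under it both cases classify correctly. This stands. Cases 1 and 2, however, do not depend on the reading.

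2. The start-date rule does not decide the class when the stop is complete. This also stands. Its harm is an impossible date order (Case 6) and, on either reading, an imputed start that feeds the stop month when both dates are partial.

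3. Partial in-trial stop dates should be uncommon. Protocol 7.4 requires start and end dates, and the Schedule of Assessments has a medication review at every visit. This is reasonable, but it limits frequency and does not make the rule right.

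4. A reader might infer that the plan's only account of background treatment is corrupted, or that the efficacy results are at risk. The documents support neither. SAP 8.4 also plans a by-patient medication listing, SAP 8.2 lists weight-loss interventions and nutritional counseling, and SAP 8.3 tabulates concomitant procedures. With 10-15 children and as-collected dates, each assignment can be checked by eye. Nothing in SAP 9 uses the prior/concomitant split.

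**Conclusion.** The point holds as a minor one. SAP 11.2 states rules that give wrong entries for some medicines with partial stop dates, and this survives the kinder reading of the missing-month cell. It also produces starts that contradict a recorded year or follow a recorded stop. The damage is limited to the descriptive prior and concomitant tables, including the interim ones. The worked cases rest on an assumed first-dose date, and the simulated rates rest on assumed enrollment, start and duration ranges. Complete stop dates are classified correctly, and a missing stop day can err only toward concomitant.

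**What to change.** Give medications their own rows in SAP 11.2:
- Keep every recorded date part.
- Impute a partial start to the earliest date, and a partial stop to the latest date, consistent with those parts. Treat the medicine as ongoing if the stop year is unknown.
- Never place an imputed start after a recorded stop.
- In SAP 8.4, call a medicine prior only if its recorded parts show that it stopped before enrollment; otherwise call it concomitant.
- Keep the on-or-after-treatment floor for AE start dates only.

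The cost is a few lines of SAP text and derivation code. There is a real trade-off. In the simulation no medicine taken during the trial was tabulated as prior, but every truly prior medicine with an unknown stop year, and about 25% of those with an unknown stop month (those that stopped in the enrollment year), were counted as concomitant. That is the conservative direction for judging what else a child was taking, and a table footnote can say so.

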### 11.3 Pooling of Centers in Multi-Center Studies

As no site-level analyses are planned, there will be no pooling of centers.

### 11.4 Multiple Comparisons/Multiplicity

No adjustments for multiple comparisons or multiplicity will be made.

### 11.5 Examination of Subgroups

Analyses by genotype may be provided.

## 12 Interim Analysis and Data Monitoring

An interim analysis is planned for 23 August 2023, the last day study day prior to the first scheduled Bridging Visit (see protocol for more information). The purpose of this analysis is to support a regulatory submission to the European Medicines Agency (EMA).

All efficacy analyses, demographics, medical history, concomitant procedures, prior medications, and concomitant medications will be created for this analysis but will only include patients that have completed or early discontinued from the study as of 23 August 2023. The results of this analysis will not be considered for the purposes of modifying the study.

## 13 Quality Control

All data displays and analyses will adhere to the International Conference on Harmonization (ICH) *Harmonized Tripartite Guideline: Structure and Content of Clinical Study Reports (ICH Topic E3)*.

All analyses will be performed using SAS® Version 9.4 (or later). [REDACTED] will follow its standard operating procedures in the creation and quality control of all tables, listings, figures, and analyses. Sponsor or its designee will review all tables, listings, and figures prior to final database lock. All final SAS programs and associated output files will be transferred to Sponsor in agreed-upon format at project completion.

## **14 Tables and Listings Conventions**

Mock-ups for statistical tables and listings will be provided. Final formats for the statistical tables and listings may deviate from these mock-ups upon agreement with the Sponsor. Footnotes will be used as needed to clarify the information that is presented in the tables and listings. Unless otherwise requested by the Sponsor, the term ‘patient’ will be used in all tables and listings, in accordance with Clinical Data Interchange Standards Consortium (CDISC) standards.

The table and listing mock shells, along with their programming convention, will be provided in a separate document.

[figure not shown]
## **15 References**

## 16 Appendices

### 16.1 Schedule of Assessments

Assessment	Screening	Enrollment Visit (Baseline)	Dose Escalation Visits 	Study Visits	End of Treatment Visit	End of Study Visit (Telephone)	Early Termination Visit
Study Week	-8 to -1		2, 4, 6	8, 12, 16, 20, 28, 36, 44 	52	56	
Study Day	-56 to -1	1	15, 29, 43	57, 85, 113, 141, 197, 253, 309	365	393	
Window			+/-3	+/-5	+/- 5	+/-3	
Informed Consent	X						
Inclusion/ Exclusion	X	X					
Genetic Sample 		X					
Medical History	X						
Physical Exam 	X	X*	X	X	X		X
Fitzpatrick classification scale		X			X		X
Comprehensive Skin Exam 	X	X		X	X		X
Weight 	X	X	X	X	X		X
Height 	X	X	X	X	X		X
Waist circumference 	X	X	X	X	X		X
Vital Signs 	X	X	X	X	X		X
ECG 	X	X	X	X 	X		X
Daily drug compliance 		X	X	X	X		
Adverse events	X	X	X	X	X	X	X
Injection site inspection		X	X	X	X		X
Concomitant medication Review	X	X	X	X	X	X	X
Optional Nutritional Counseling 		X	X	X	X		
Bone Age 		X			X		
Ages & Stages Questionnaires, Third Edition (ASQ- 3) 		X		X	X		

Assessment	Screening	Enrollment Visit (Baseline)	Dose Escalation Visits 	Study Visits	End of Treatment Visit	End of Study Visit (Telephone)	Early Termination Visit
Study Week	-8 to -1		2, 4, 6	8, 12, 16, 20, 28, 36, 44 	52	56	
Study Day	-56 to -1	1	15, 29, 43	57, 85, 113, 141, 197, 253, 309	365	393	
Window			+/-3	+/-5	+/- 5	+/-3	
Safety Lab Tests 	X	X	X	X 	X		X

[figure not shown]
[figure not shown]

Anti-Drug Antibodies 	X			X 	X		X
PK profile 		X 		X 			X
Trough PK 			X	X 	X		
Dispense Study Drug		X	X	X			
Return Study Drug			X	X	X		
Optional Informed Consent for Exit Interviews					X		

Abbreviations: ECG=Electrocardiogram

Note: If there are <2 weeks between screening and enrollment, the enrollment visit physical examination may be waived.

1. A complete physical examination will be conducted at screening and at the End of Treatment (EOT) Visit. At other timepoints, an abbreviated examination will be performed. The abbreviated examination should focus on heart, lungs, skin, neurologic exam, and any areas of previous abnormal findings, noting any changes from baseline. Tanner staging should be performed at Screening and at the EOT (Week 52) visit. It may be done at additional visits, at the discretion of the Investigator.
2. A comprehensive skin evaluation will be performed by the Investigator or qualified designee. The skin exam should include a full body skin exam (head-to-toe skinexamination). Any concerning lesions identified during the Screening Period will be biopsied and results known to be benign prior to first dose of setmelanotide. If the pre-treatment biopsy results are of concern, the patient will be excluded from the study. Additionally, any new lesion or change in an existing lesion identified during the course of the study must be evaluated by a dermatologist and biopsied, if clinically indicated in the opinion of the dermatologist.
3. Weight (kg) is to be measured at the clinic using the same scale throughout the study or at home (during virtual visits or visiting nurse visits) using the same scale provided to the patient as part of the clinical study. Weight should be measured after patients have attempted to empty their bladders and after fasting for at least 8 hours. Patients are to wear light clothing or underwear and no shoes, with empty pockets, and will be weighed at approximately the same time of day. All measurements will be recorded to the nearest tenth kg if reported with a digital scale, or half Kg with a mechanical scale.
4. Height (cm) will be measured, without shoes, socks or hats, using a wall-mounted stadiometer. The stadiometer should be calibrated by site personnel on a daily basis prior to height assessment. All measurements will be done in triplicate at each time point and recorded to the nearest half cm.
- 5.
6. All blood pressure (BP) and heart rate (HR) measurements are to be obtained in a sitting position following at least 5 minutes of rest. All measurements will be taken in triplicate, approximately 2 minutes apart. When possible, BP should be taken in the non-dominant arm using the same methodology (automated or manual) throughout the study.
7. A single 12-lead ECG will be performed. If an ECG is not practical in a young patient, it may be replaced by a rhythm strip and HR and PR interval should be documented.
8. A daily question querying whether the patient completed their daily injection will be asked via electronic diary. Paper versions can be used, if required.
9. Safety laboratory tests will include CBC with platelet count and standard indices, chemistry panel (includes sodium, potassium, chloride, CO2, albumin, total protein, glucose, BUN, creatinine, uric acid, aspartate aminotransferase (AST), alanine aminotransferase (ALT), gamma-glutamyl transferase (GGT), creatine phosphokinase (CPK), alkaline phosphatase, total bilirubin, direct bilirubin, lactate dehydrogenase (LDH), calcium, phosphorus), thyroid-stimulating hormone (TSH) and urinalysis with microscopic analysis if positive findings on dipsticks warrant further examination. If there is a marginal value close to the exclusion range, it is suggested to repeat the laboratory analyses at Investigator's discretion. To allow for pre- and post-dose sampling, patients will attend the site visit having fasted for an 8-hour time period without injecting the trial product. On the day of the site visit, dosing will be conducted on site. The Investigator's will adhere to the site-specific blood volume limits for safety laboratory and PK analyses to ensure minimal distress to the pediatric patients. Due to the age of the children, it may not be possible to collect all labs at every study visit. Screening may be performed over multiple days, to complete the required assessments. After enrollment, if all lab tests are not possible, then the tests should be collected in the following descending order of priority: safety, anti-drug antibodies, trough PK, hemoglobin A1c and then lipid panel. If it is not possible to collect the safety labs on two consecutive visits, the patient should be discussed with the Sponsor. If the genetics sample cannot be collected at the enrollment visit, it may be collected during a later study visit. Anti-drug antibody samples are to be collected prior to dosing with setmelanotide. If PK profile cannot be obtained due to logistical challenges, the Investigator should aim to at least obtain sample trough PK.
- 10.
- 11.

- 12. 
  - 13. 
  - 14. Based on the age and status of the patient, optional nutritional counseling may be requested by the Investigator, either during the enrollment visit or at any other time during the study. For pediatric patients, nutritional counseling will be performed by an appropriate dietician or nutritionist (or equivalent) to ensure that pediatric patients have adequate nutritional intake to maintain proper growth and development.
  - 15. Bone age may be read locally initially, but the Sponsor may request central reading of images. A standard bone age measurement (of the hand/wrist area) will be obtained at the beginning and the end of the study to monitor for growth related safety concerns.
  - 16. The ASQ-3 is intended for use at six-month intervals between 6 months and 3 years of age, and then at one-year intervals through age 5. Thus, for patients who enter the study at ages between 2 years and 3 years, the ASQ-3 should be administered at the Baseline Visit, Week 28 visit and End-of-Treatment Visit. For patients who enter the study between the ages of 3 and 6 years old, the ASQ-3 should only be administered at the Baseline Visit and End-of-Treatment Visit.
  - 17. The dose may continue to be evaluated and adjusted, at the discretion of the Investigator, in 0.5 mg increments, so long as the daily dose is kept between 0.5 mg and the weight-based maximum for the patient (see [Table 3](#)).
- 

## 16.2 Changes in Analysis Planned in the Protocol

### Changes in Analysis Planned in the Protocol

CSP Section	SAP section	Description/Rationale of Change

## 16.3 Change History

The table below outlines the changes made to the SAP since the previous version.
